11.2.1.1 Consultation with Medical Monitor and local hepatologist

Potential drug-induced liver injury events require notification of the Medical Monitor within 24 hours (eg, by laboratory alert), and the subject must be discussed with the Medical Monitor as soon as possible. If required, the subject must also be discussed with the local hepatologist. The local hepatologist is the expert usually consulted by the treating physician for assessment and management of potential hepatic disease. This would usually be a hepatologist, but may be a gastroenterologist. If determined necessary, this discussion should be followed by a full hepatology assessment (see [Section 11.2.1.4](#)) and SAE report (if applicable).

11.2.1.2 Immediate action: determination of investigational medicinal product discontinuation

All PDILI events require immediate action, testing, and monitoring.

The immediate action is dependent on the laboratory values and symptoms of hepatitis or hypersensitivity and ranges from continuation of IMP (followed by immediate investigation) to immediate and permanent discontinuation (see [Section 6.3.1](#) and [Table 11-3](#) for details).

When IMP is discontinued, all concomitant medications and herbal supplements that are not medically necessary should also be discontinued. The Investigator should also consider dose reduction for medically necessary concomitant medication and consider changing any medically required concomitant medication known to be hepatotoxic to a suitable alternative.

11.2.1.3 Investigational medicinal product restart/rechallenge

Rechallenge with a substance potentially causing drug-induced liver injury is dangerous, may be fatal, and must not occur.

11.2.1.4 Testing: identification/exclusion of alternative etiology

The measurements and additional information required for the assessment of PDILI events when there is a reasonable possibility that they may have been caused by the IMP are detailed in [Table 11-4](#) (laboratory measurements) and [Table 11-5](#) (additional information). Results of the laboratory measurements and information collected are to be submitted to the Sponsor on the corresponding eCRF. If the medical history of the subject indicates a requirement for other assessments not included below, these additional assessments should be completed and submitted, as applicable.

All blood samples should be stored, if possible. If tests are done locally for more rapid results, a concurrent sample must also be sent to the central laboratory.

The measurements to be assessed are detailed in [Table 11-4](#).

Table 11–4: PDILI laboratory measurements

Virology-related	Hepatitis A IgM antibody
	HBsAg
	Hepatitis E IgM antibody
	HBcAb-IgM
	Hepatitis C RNA
	Cytomegalovirus IgM antibody
	Epstein-Barr viral capsid antigen IgM antibody (if unavailable, obtain heterophile antibody or monospot testing)
Immunology	Anti-nuclear antibody (qualitative and quantitative)
	Anti-smooth muscle antibody (qualitative and quantitative)
	Type 1 anti-liver kidney microsomal antibodies (qualitative and quantitative)
Hematology	Eosinophil count
Urinalysis	Toxicology screen ^a
Chemistry	Amylase
	If total bilirubin $\geq 1.5 \times \text{ULN}$, obtain fractionated bilirubin to obtain % direct bilirubin
	Serum CPK and LDH to evaluate possible muscle injury causing transaminase elevation
Additional	Prothrombin time/INR ^b
	Serum pregnancy test
	PK sample

ALT=alanine aminotransferase; CPK=creatine phosphokinase; HBcAb-IgM=hepatitis B core antibody-IgM; HBsAg=hepatitis B surface antigen; IgM=immunoglobulin M; INR=international normalized ratio; LDH=lactate dehydrogenase; PDILI=potential drug-induced liver injury; PK=pharmacokinetic; RNA=ribonucleic acid; ULN=upper limit of normal

^a For detecting substances (ie, amphetamines, benzodiazepines, opioids, marijuana, cocaine, phencyclidine, and tricyclic antidepressants), additional tests may be performed based on the Investigator’s medical judgment and subject’s history.

^b Measured only for subjects with ALT $> 8 \times \text{ULN}$, elevations in total bilirubin, and symptoms of hepatitis or hypersensitivity. Hepatitis symptoms include fatigue, nausea, vomiting, and right upper quadrant pain or tenderness; hypersensitivity symptoms include eosinophilia ($> 5\%$), rash, and fever (without clear alternative cause).

The following additional information is to be collected (Table 11–5).

Table 11–5: PDILI information to be collected

New or updated information
Concomitant prescription and over-the-counter medications (eg, acetaminophen/paracetamol, herbal remedies, vitamins); dosages and dates should be included
Pertinent medical history, including the following: 
 • History of liver disease (eg, autoimmune hepatitis, nonalcoholic steatohepatitis or other “fatty liver disease”) • Adverse reactions to drugs • Allergies • Relevant family history or inheritable disorders (eg, Gilbert’s syndrome, alpha-1 antitrypsin deficiency) • Recent travel • Progression of malignancy involving the liver (Note: Metastatic disease to the liver, by itself, should not be used as an explanation for significant AST and/or ALT elevations)
The appearance or worsening of clinical symptoms of hepatitis or hypersensitivity (eg, fatigue, nausea, vomiting, right upper quadrant pain or tenderness, decreased appetite, abdominal pain, jaundice, fever, or rash)
Recent clinically significant hypotension or hypoxemia with compromised cardiopulmonary function
Alcohol and illicit drug use
Results of liver imaging or liver biopsy, if done
Results of any specialist or hepatology consult, if done
Any postmortem/pathology reports

ALT=alanine aminotransferase; AST=aspartate aminotransferase; PDILI=potential drug-induced liver injury

11.2.1.5 Follow-up evaluation

Potential drug-induced liver injury events require follow-up monitoring as described in [Table 11-3](#). Monitoring should continue until liver chemistry values normalize, stabilize, or return to Baseline. Determination of stabilization is at the discretion of the Investigator in consultation with the hepatologist (as applicable) and UCB responsible physician, as needed.

11.3 Other safety measurements

11.3.1 Assessment and management of tuberculosis and tuberculosis risk factors

All subjects will be assessed for TB prior to administration of IMP and at the time points specified in the Schedule of Assessments ([Table 5–1](#)) through physical examination for signs and symptoms of TB, laboratory testing ([Section 11.3.1.1](#)), CXR ([Section 11.3.1.2](#)), and subject questionnaire ([Section 11.3.1.3](#)).

Prior to administration of IMP, subjects will have an IGRA test (QuantiFERON TB GOLD is recommended), a CXR or CAT scan of chest (unless already performed within 3 months of Screening), and examination for signs and symptoms of TB unless an IGRA negative result is

available less than 4 weeks prior to the first dose of IMP. In addition, each subject will complete a TB questionnaire with questions directed at symptoms of TB and potential exposure to TB.

Test Conversion

Tuberculosis test conversion is defined as a positive IGRA result for the current test when previous IGRA test results are negative. All subjects with TB test conversion must immediately stop IMP administration. In case of a TB test conversion, the subject must be considered as having either a suspected new latent or an active TB infection and be promptly referred to an appropriate specialist (eg, pulmonologist, infectious disease specialist) for further evaluation. If the test conversion indicates LTB infection, active TB, or NTMB then, per UCB TB working instructions, TB test conversion (confirmed) should be classified adequately, either as due to LTB infection, active TB infection, or NTMB, respectively. Additional assessments (eg, blood tests or IGRA, CXRs, or other imaging) should be performed where medically relevant and documented. Such conversions should be reported to the UCB PS function.

Latent TB

In case the evaluation by the appropriate specialist indicates a new LTB infection during the study, a prophylactic TB treatment should be initiated and the IMP can be continued no sooner than 4 weeks after start of prophylactic TB treatment, if it is deemed likely by the Investigator that prophylactic TB treatment is continued to completion.

If prophylaxis is not initiated, the subject must be withdrawn.

Every related action should be discussed in advance with the Medical Monitor and/or UCB Study Physician.

Once withdrawn from IMP, subjects should return for the Early Withdrawal Visit and complete a SFU Visit (20 weeks after the last dose of IMP).

Active TB or NTMB infection

Subjects who develop active TB or NTMB infection during the study must be withdrawn from the study. The subject must be immediately discontinued from IMP and an Early Withdrawal Visit must be scheduled as soon as possible, but no later than the next scheduled visit. The subject should be encouraged to attend the SFU Visit as specified by the protocol. Treatment should be started immediately.

Note that subjects with history of NTMB or active NTMB infection are excluded from the study regardless of prior or current therapy for this condition.

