6.3 Withdrawal criteria

Subjects are free to withdraw from the study at any time, without prejudice to their continued care.

Subjects should be withdrawn from the study and encouraged to come for the SFU Visit (20 weeks after the last dose of IMP) if any of the following events occur:

1. Subject withdraws his/her consent.
2. The Sponsor or a regulatory agency requests withdrawal of the subject.

Subjects should be withdrawn from all IMP and will be asked to return for the study assessments 12 weeks after the first dose (ie, the Week 12 Visit) and for the SFU Visit (20 weeks after the last dose of IMP) if any of the following events occur:

1. There is confirmation of a pregnancy during the study, as evidenced by a positive pregnancy test.
2. Subject develops an illness that would interfere with his/her continued participation.
3. Subject considered to have either a suspected new LTBI infection or who develops active TB or NTM infection during the study (including but not limited to conversion demonstrated by IGRA or other diagnostic means) must be immediately discontinued from IMP and an Early Withdrawal Visit must be conducted as soon as possible, but not later than the next regular visit.

Confirmed active TB is an SAE and must be captured on an SAE Report Form and provided to the Sponsor in accordance with SAE reporting requirements. As with all SAEs, periodic follow-up reports should be completed as per protocol requirements until such time as the TB infection resolves.

Additional information on TB policies are provided in [Section 11.3.1](#).

4. Subject is noncompliant with the study procedures or medications in the opinion of the Investigator.
5. Subject uses prohibited concomitant medications, with the exception of topicals, as defined in this protocol ([Section 7.8.2](#)), that may present a risk to the safety of the subject in the opinion of the Investigator and/or the Medical Monitor and/or UCB Study Physician.
6. Subject develops total bilirubin $>2 \times \text{ULN}$ (except Gilbert's); neutropenia $<1.0 \times 10^9/\text{L}$; lymphopenia $<0.5 \times 10^9/\text{L}$.
7. Subject has active suicidal ideation as indicated by a positive response ("Yes") to questions 4 or 5 or to the suicidal behavior questions of the "Since Last Visit" version of the self-rated C-SSRS. The subject should be referred immediately to a Mental Healthcare Professional and must be withdrawn from the study.

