11.3.1.1 Tuberculosis assessment by interferon-gamma release assay

During conduct of the study, the TB assessment by IGRA (QuantiFERON TB GOLD is recommended) will be performed at study entry (unless an IGRA negative result is available less than 4 weeks prior to the first dose of IMP). The test results will be reported as positive, negative, or indeterminate. UCB also recommends that a TB specialist be consulted where TB (latent or active) is suspected or if there are doubts regarding test results. If latent or active TB is identified, subject must undergo appropriate study-specified withdrawal procedures.

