11.3.1.3 Tuberculosis questionnaire

The questionnaire "Evaluation of signs and symptoms of tuberculosis" should be used as a source document. The questionnaire will be completed at study entry and at all visits specified in Table 5-1. The questionnaire will assist with the identification of subjects who may require therapy for TB. A subject who answers "Yes" to the question [REDACTED]

[REDACTED] at HS0001 entry is excluded. A "Yes" response to any of the other questions within the questionnaire at HS0001 entry should trigger further careful assessment to determine if subject has LTB or active TB. A "Yes" response to any of the questions during the study should trigger further assessments to determine if the subject has either LTB or active TB infection.

Subjects with a latent or active TB infection must be withdrawn from the study.

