11.3.1.4 Tuberculosis management

LTB infection and active TB identified during study

During the study, subjects who develop evidence of LTB infection or active TB must immediately stop further administration of IMP and will be referred to an appropriate TB specialist (pulmonologist or infectious disease specialist) for further evaluation. Evidence of LTB infection is defined as subject's IGRA test converts to positive or indeterminate (and confirmed indeterminate on repeat), or the subject's questionnaire or history and physical indicates that TB infection or exposure may have occurred. Evidence of active TB includes, in addition to the aforementioned tests, signs, and symptoms of organ involvement. In either situation, the subject should be carefully assessed by a TB specialist for active TB. Subjects diagnosed with active TB or LTB infection should be withdrawn from the study and receive appropriate TB or prophylaxis therapy.

If a TB specialist excludes an active TB infection the subject can proceed with the IMP no earlier than 4 weeks after the start of an appropriate prophylactic therapy.

Any presumptive diagnosis or diagnosis of a TB infection is a reportable event. Confirmed active TB must be reported as an SAE. The Investigator is to complete and submit the TB follow-up form provided.

The subject should be transferred to the care of his/her physician and managed according to the best available standard of care. Subjects identified as having converted to active TB during the study must be withdrawn and scheduled to return for the Early Withdrawal Visit as soon as possible, but no later than the next scheduled study visit and complete all Early Withdrawal Visit assessments.

The subject should be encouraged to complete a SFU Visit (20 weeks after the last dose of IMP).

If infection with NTMB is identified during the study, the same procedure as for active TB acquired during the study must be followed.

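### The protocol both allows and rules out restarting study drug after latent TB found on treatment; the HADS entry rule and the pregnancy-test schedule also need small alignments

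*Protocol*

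**What the plan says.** **Latent TB.** Under its latent TB heading, Protocol Section 11.3.1 says to start prophylaxis and that "the IMP can be continued no sooner than 4 weeks after start of prophylactic TB treatment", provided the Investigator thinks the course is likely to be completed. It adds: "If prophylaxis is not initiated, the subject must be withdrawn". It also asks that every related action be discussed beforehand with the Medical Monitor and/or Study Physician. Section 11.3.1.3 says: "Subjects with a latent or active TB infection must be withdrawn from the study". Section 11.3.1.4 says: "Subjects diagnosed with active TB or LTB infection should be withdrawn from the study and receive appropriate TB or prophylaxis therapy". Its next sentence says that, if a specialist excludes active TB, "the subject can proceed with the IMP no earlier than 4 weeks after the start of an appropriate prophylactic therapy". Withdrawal criterion 3 in Section 6.3 covers suspected new latent infection: the subject "must be immediately discontinued from IMP and an Early Withdrawal Visit must be conducted as soon as possible". It then points back to Section 11.3.1 ("Additional information on TB policies are provided in").

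**HADS.** Exclusion 23 in Section 6.2 bars entry on HADS scores only when HADS-D is at least 10 and HADS-A is at least 15. Withdrawal criterion 8 in Section 6.3 mandates withdrawal at HADS-D of 15 or more, whatever the HADS-A score. Section 9.11 classes 15 and above as severe.

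**Pregnancy tests.** Section 11.3.2 asks for a negative urine test right before each IMP administration. Table 5-1 and the Section 8 visit lists schedule tests at Screening, Baseline, Weeks 4, 8 and 12, and Safety Follow-Up (SFU).

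**The concern.** These rules decide who receives study drug. With latent TB, a site that wants to restart and a site that withdraws the subject can each cite current protocol text. The Medical Monitor or Study Physician who is consulted has no single rule to apply.

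With HADS, a subject can pass the entry score rule at a depression score that the same protocol calls severe and treats as mandatory withdrawal. A site that reads criterion 8 as a post-Baseline rule could dose that subject. Section 6.4.1 also calls a Data Monitoring Committee (DMC) meeting once more than one subject meets criterion 3, 7, 8, 9 or 10. Read literally, a score present at entry could count toward that without any drug effect.

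With pregnancy tests, a site that works from the visit lists alone would miss tests that Section 11.3.2 asks for.

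**Working it through.** The plan states no figure to reproduce here. The check compares the rules and counts visits.

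**1. Latent TB: the texts side by side.** Take a subject with new latent TB, no active TB, and prophylaxis started.

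| Text | What happens to this subject |
|---|---|
| 11.3.1, latent TB | IMP may resume after 4 weeks or more; not withdrawn |
| 11.3.1.3 | Withdrawn from the study |
| 11.3.1.4, withdrawal sentence | Withdrawn from the study, given prophylaxis |
| 11.3.1.4, next sentence | IMP may resume after 4 weeks or more |
| 6.3, criterion 3 | IMP stopped; no restart mentioned; refers to 11.3.1 |

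Separating latent from active disease does not reconcile these, because the withdrawal sentences name latent TB. Section 11.3.1.1 also says "If latent or active TB is identified, subject must undergo appropriate study-specified withdrawal procedures", but it describes the test at study entry, so I give it little weight.

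**2. Latent TB: how often it could arise.** Table 5-1 schedules the interferon-gamma release assay (IGRA) at Screening and SFU, and the TB questionnaire at Screening, Baseline, Week 12 and SFU. The last dose is at Week 10. No TB test or questionnaire is scheduled between the first and last dose, so detection in that window would be unscheduled.

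**3. Latent TB: what a restart could deliver.** Active bimekizumab is given at Weeks 0, 2, 4, 6, 8 and 10 (6 doses). Active adalimumab is given at Weeks 0, 2, 4, 5, 6, 7, 8, 9 and 10 (9 doses). Assume that IMP stops and prophylaxis starts at the Week *w* visit, with that visit's dose not given. The earliest restart is then Week *w* + 4.

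| *w* | Earliest restart | Bimekizumab doses left | Adalimumab doses left | Days since last active bimekizumab dose |
|---|---|---|---|---|
| 2 | Week 6 | 3 (Weeks 6, 8, 10) | 5 (Weeks 6 to 10) | (6 − 0) × 7 = 42 |
| 4 | Week 8 | 2 (Weeks 8, 10) | 3 (Weeks 8, 9, 10) | (8 − 2) × 7 = 42 |
| 6 | Week 10 | 1 (Week 10) | 1 (Week 10) | (10 − 4) × 7 = 42 |
| 7 or later | Week 11 or later | 0 | 0 | not applicable |

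If prophylaxis starts later than the stop, fewer doses remain. Section 8 caps the time between doses at 18 days. Even if a dose were given on the day prophylaxis began, the gap would be 4 × 7 = 28 days, so every permitted restart breaks the cap.

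**4. HADS.** Each subscale runs from 0 to 21 (Section 9.11). Criterion 8 covers HADS-D 15 to 21, which is 7 values. Paired with 22 HADS-A values, that gives 7 × 22 = 154 score pairs.
- HADS-A 15 to 21: 7 × 7 = 49 pairs, excluded at entry by exclusion 23.
- HADS-A 0 to 14: 7 × 15 = 105 pairs, not excluded by score.

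These count score combinations, not subjects.

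**5. Pregnancy tests.** Dosing visits are Weeks 0, 2, 4, 5, 6, 7, 8, 9 and 10, which is 9. Tests fall on Weeks 0, 4 and 8, which is 3. The other 9 − 3 = 6 (Weeks 2, 5, 6, 7, 9, 10) have none, in Table 5-1 or in Sections 8.3, 8.5, 8.6 and 8.8. Those six visits carry 3 of 6 active bimekizumab doses (Weeks 2, 6, 10) and 6 of 9 active adalimumab doses. The scheduled interval between tests during dosing is 4 weeks.

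**The case against.** **Latent TB.** Sections 6.3, 11.3.1 and 11.3.1.4 all stop IMP at once, and 11.3.1 puts a prior medical discussion in front of any further step. Criterion 3 also sits in a list whose lead-in withdraws subjects from all IMP. This stands, and it narrows the conflict to later resumption. It does not remove the conflict, because criterion 3 refers the reader back to 11.3.1, where resumption is allowed. A reader might infer that subjects with latent TB would go on being dosed without interruption, or that a site could restart on its own authority. Neither is supported.

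The 18-day cap could be taken as showing that no restart was intended. It is loosely worded, though: its 12-day minimum cannot hold for the weekly injections, and Section 8 lets changes outside the visit window be discussed. It cannot settle the point.

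**HADS.** A reader might infer that HADS-D of 15 or more never bars entry. It does when HADS-A is also 15 or more. Nor does the gap show that such a subject must be dosed: read literally, criterion 8 would withdraw the subject first, although its list brings subjects back 12 weeks after the first dose and so seems to presuppose dosing. Inclusion 12 and exclusion 30 allow refusal on judgement, and HADS-D of 10 or more triggers mental-health referral. What remains is that no entry score rule requires refusal.

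**Pregnancy tests.** A reader might call this a contradiction. It is not, because doing the extra tests satisfies both texts. The Table 5-1 and Table 11-2 footnotes about urine testing at other visits can be read as stating only the specimen type, so the mismatch rests on the Section 11.3.2 sentence. Highly effective contraception, two negative tests before the first dose and 4-weekly testing limit the risk.

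**Conclusion.** The latent TB rule is wrong as written: current protocol text gives two answers on resuming IMP for the same subject, and the documents do not show which was meant. Its reach is small. It needs unscheduled detection and prophylaxis by about Week 6, with at most 3, 2 or 1 bimekizumab doses or 5, 3 or 1 adalimumab doses left for a start at Week 2, 4 or 6. Those counts assume that IMP stops and prophylaxis starts at the same visit.

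The HADS item is an entry gap limited to HADS-D 15 to 21 with HADS-A 0 to 14, and closing it is a cheap improvement. The pregnancy item is a schedule alignment. How many subjects the TB or HADS items would touch cannot be derived from the documents.

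Overall severity is minor. A reader might infer that the trial's efficacy conclusion is at risk; nothing here changes the sample size, the analysis or the success criterion.

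**What to change.** 1. **Latent TB.** In Section 11.3.1, replace both the resume sentence and the sentence that withdraws only subjects without prophylaxis with: *Prophylactic TB treatment should be initiated, IMP must be permanently discontinued, and the subject follows the withdrawal procedures in Section 6.3.* Delete the resume sentence in Section 11.3.1.4. Deleting the two resume sentences alone would not be enough: it would remove the 11.3.1 instruction to start prophylaxis and leave a sentence implying that a treated subject stays on IMP. Permanent discontinuation is the conservative choice, since few doses could remain and exclusion 16 already bars latent TB at entry. If resumption was intended, amend instead Section 11.3.1.3, the withdrawal sentence in 11.3.1.4 and criterion 3, and add an exception to the 18-day interval in Section 8.
2. **HADS.** Add HADS-D of 15 or more at Screening or Baseline to Section 6.2 as a stand-alone exclusion, checked before randomization. HADS is already collected at both visits; the downside is a few more screen failures.
3. **Pregnancy tests.** Add the urine test at Weeks 2, 5, 6, 7, 9 and 10 in Table 5-1 and Sections 8.3, 8.5, 8.6 and 8.8. If 4-weekly testing was intended, amend Section 11.3.2 to the scheduled visits.

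The cost is one minor protocol amendment and a site memo, plus up to six extra urine tests per woman of childbearing potential under the first option in item 3.
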